#### **11.1.7.2 Analytical Method**

Assessment of ADA will be performed by Haemtech Biopharma Services, Inc. refer to [Section 3](#).

#### **11.1.8 Adverse Events**

##### **11.1.8.1 Adverse Event Definition**

An AE means any untoward medical occurrence associated with the use of a drug in humans, whether or not considered drug related.

A suspected adverse reaction means any AE for which there is a reasonable possibility that the drug caused the AE. Reasonable possibility means there is evidence to suggest a causal relationship between the drug and the AE.

An AE can therefore be any unfavorable and unintended sign (including an abnormal laboratory finding), symptom, or disease temporally associated with the use of a medicinal (investigational) product, whether or not related to the medicinal (investigational) product [7].

##### **11.1.8.2 Monitoring**

Subjects will be monitored throughout confinement for adverse reactions to the study drug and/or procedures. Subjects will be asked how they are feeling and encouraged to report AEs during confinement and at each follow-up visit.

AEs (whether serious or non-serious) and clinically significant abnormal laboratory test value(s) will be evaluated by the PI or designee and treated and/or followed up until the symptoms or value(s) return to normal, or acceptable levels, as judged by the PI or designee.

Treatment of SAEs will be performed by a physician, either at Celerion or at a nearby hospital emergency room. Where appropriate, medical test(s) and/or examination(s) will be performed to document resolution of event(s). Outcome may be classified as resolved, improved, unchanged, worse, fatal, or unknown (lost to follow-up).

### 11.1.8.3 Reporting

All AEs that occurred during this clinical trial will be recorded. AEs will be coded using the most current version of MedDRA® available at Celerion.

The PI or designee will review each event and assess its relationship to drug treatment (unrelated, unlikely, possibly, probably, or likely,). Each sign or symptom reported will be graded on the FDA (Center for Biologics Evaluation and Research) toxicity grading scale for healthy volunteers 4-point severity scale (Grade 1, 2, 3 and 4) [8]. The date and time of onset, time relationship to drug dosing, duration, and outcome of each event will be noted.

#### Relationship of AE:

The relationship of each AE to the study drug will be assessed using the following definitions:

Unrelated	

▪ The adverse event must clearly be caused by the participants clinical state, or the study procedure/conditions

▪ Definitely not related to drug

▪ Temporal sequence of an adverse event onset relative to administration of drug not reasonable

▪ Another obvious cause of an adverse event

Unlikely	

▪ Time sequence is unreasonable

▪ There is another more likely cause for an adverse event

Possibly	

▪ Corresponds to what is known about the drug

▪ Time sequence is reasonable

▪ Could have been due to another equally, likely cause

Probably	

▪ Is a known effect of the drug

▪ Time sequence from taking drug is reasonable

▪ Ceases on stopping the drug

▪ Cannot be reasonably explained by the known characteristics of the participants clinical state

Likely	

▪ Is a known effect of the drug (e.g. listed in IB)

▪ Time sequence from taking drug is reasonable

▪ Event stops upon stopping drug, event returns upon restarting drug

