### **8.2 Background**

#### **8.2.1 Preclinical Trials**

The molecular mechanism by which E-WE thrombin exerts its antithrombotic activity is the selective activation of endogenous plasma protein C under intravascular shear flow. Antithrombotic treatment with E-WE thrombin utilizes an endogenous targeting system via cell-surface associated thrombin receptors including, among others, thrombomodulin, glycoprotein Ib [2], and PARs, which are variably expressed on the luminal surfaces of blood vessels, platelets, and other cells. One of the putative mechanisms of action, *in vivo*, is binding of E-WE thrombin to circulating platelets, which deliver and concentrate E-WE thrombin on the thrombus, which is the site of desired pharmacological activity. At the thrombus interface, E-WE thrombin cleaves protein C, generating the potent endogenous antithrombotic and anti-inflammatory enzyme APC, thereby downregulating thrombin generation and interrupting thrombogenesis. APC exerts additional protective effects by upregulating cytoprotective mechanisms and promoting anti-apoptotic signaling through cleavage of the transmembrane receptors, such as PAR 1 and 3.

In both mice and primates, E-WE thrombin has potent antithrombotic effects, with concomitant hemostatic safety. The efficacy of E-WE thrombin has been established in several experimental models, including a mouse model of stroke [3], a mouse model of myocardial ischemia and reperfusion, and a well-established model of vascular graft thrombosis in baboons [4], alone and in combination with fibrinolysis. Importantly, while treatment with E-WE thrombin was efficacious in these experimental models, no demonstrable effect of E-WE thrombin on hemostasis was observed. These data indicate that, in contrast to currently marketed antithrombotics, which target elements of the coagulation cascade that participate in or are essential for both thrombosis and hemostasis, E-WE thrombin targets thrombosis without increasing bleeding.

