### **8.2.5 Toxicology**

The toxicity profile of E-WE thrombin was evaluated in two GLP single-dose acute toxicity studies in Sprague-Dawley rats and cynomolgus monkeys. In rats, a single dose of E-WE thrombin was administered at doses of 0, 30, 100, and 300 mcg/kg and animals were evaluated for 3 days (main study) and 29 days (recovery group) after dosing. In cynomolgus monkeys, a single dose of E-WE thrombin was administered at doses of 0, 12.5, 25, and 50 mcg/kg and animals were evaluated for 4 days (main study) and 15 days (recovery study) after dosing. E-WE thrombin was well tolerated in both species and no E-WE thrombin-related AE were observed. Based on these results, the no observed adverse effect level (NOAEL) was determined to be 300 mcg/kg/dose and 50 mcg/kg/dose, for rats and cynomolgus monkeys, respectively.

Refer to the Investigator's Brochure (IB) for detailed background information on study drug [1].

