#### **10.4.1.4 Dose Escalation and Stopping Rules**

Dose escalation to the next dose level (i.e., next cohort) will not take place until after the PI has reviewed the safety data. If any findings in the safety data are of concern, then the SRC comprised of but not limited to, the Sponsor, medical monitor, and the PI will convene to determine if adequate safety and tolerability from the previous cohort has been demonstrated to permit proceeding to the next cohort. The SRC review of all pertinent blinded safety/tolerability data must comprise of physical examinations, ECGs, vital signs, clinical laboratory tests [including coagulation], thrombin time, injection site reaction, and AEs available for all subjects who have completed up to Day 14 procedures.

Data from all subjects in the cohort will be used and reviewed for a dose escalation decision and a minimum of 4 subjects must complete the study (up to Day 14) before proceeding to the next higher dosing cohort.

Together they will make one of the following determinations:

1. To continue with the study as planned.
2. To continue with the study and add additional safety evaluations.
3. To continue with the study and repeat a cohort.

4. To continue with the study by adjusting to an intermediate dose between the current dose and the previous lower dose (i.e., add an additional cohort) or to repeat a cohort, if:
  - a. At least 1 subject has a SAE or visit to the emergency room deemed to be possibly study drug related (see [Section 11.1.8.4](#)).
  - b. At least 25% of subjects in a cohort experience a grade  $\geq 2$  AE deemed to be possibly related to the study drug.
5. To stop the study. The study will be terminated if the following number of subjects meet any of the following criteria and the subjects were determined to have received active drug after unblinding:
  - I.  $\geq 1$  subject that receive drug in a cohort experience:
    - a. Life-threatening hypersensitivity reactions (e.g., anaphylaxis, respiratory symptoms, hypotension etc.).
    - b. Any grade thromboembolic event possibly related to the study drug.
    - c. Any grade bleeding possibly related to the study drug.
    - d. Presence of antibodies against human thrombin or prothrombin.
    - e. Presence of ADA.
  - II.  $\geq 2$  subjects that receive drug in a cohort:
    - a. Has a drug possibly or probably related SAE (see [Section 11.1.8.4](#)).
    - b. Experiences a drug related grade  $\geq 3$  toxicity (see [Section 11.1.8.3](#)).

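### Every related category in the causality scale refers to what is already known about the drug, so a novel event with plausible timing has no clear rating in this first-in-human trial

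*Protocol*

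**What the plan says.** Protocol 11.1.8.3 has the investigator place each adverse event on a five-level scale. Each level is defined by a short bullet list under Relationship of AE.

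- **'Possibly'** lists "Corresponds to what is known about the drug", a reasonable time sequence, and "Could have been due to another equally, likely cause".
- **'Probably'** and **'likely'** both begin with the event being a known effect; 'likely' gives listing in the investigator's brochure (IB) as an example. 'Likely' ends with "Event stops upon stopping drug, event returns upon restarting drug".
- **'Unlikely'** lists unreasonable timing and a more likely cause elsewhere.
- **'Unrelated'** has four bullets, which exclude the drug, point to another cause, or point to implausible timing.

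The table does not say whether a level needs all of its bullets or any of them.

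Protocol 11.1.8.1 applies a different test: "A suspected adverse reaction means any AE for which there is a reasonable possibility that the drug caused the AE". Protocol 11.1.8.4, in defining unexpected events, includes suspected reactions that the IB does not list.

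On what is known, the synopsis describes a first-in-human study. Section 8.2.5 reports that "E-WE thrombin was well tolerated in both species and no E-WE thrombin-related AE were observed", and 8.2.1 that "no demonstrable effect of E-WE thrombin on hemostasis was observed".

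The rating is then used in Protocol 10.4.1.4, for example in criterion 5.I.b, "Any grade thromboembolic event possibly related to the study drug". It is also used in SAP 8.3 and Table 14.3.1.3, which break treatment-emergent events (TEAEs) down by the same five levels.

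**The concern.** The primary objective is safety and tolerability in people who have never received this drug, so the trial must be able to classify effects nobody has yet described. A scale whose related end is anchored to known effects suits that task badly. The protocol's summary offers no human experience and no drug-related animal toxicity as a reference.

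What is at stake is whether a surprising event enters the counts that bear on escalation and stopping, and how it appears in the relationship table. Several of those counts turn on one or two subjects, so a single event left without a clear rating can decide whether a criterion is met.

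**Working it through.** **Step 1: run a test event through the table.** Take a novel event with reasonable timing and no better explanation. Because the documents give no combination rule, try each reading.

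| Level | All bullets needed | Any bullet enough |
|---|---|---|
| Unrelated | not met | not met |
| Unlikely | not met: timing is reasonable, no more likely cause | not met |
| Possibly | not met if the event does not fit what is known | met on timing |
| Probably | not met: not a known effect | met on timing |
| Likely | not met: not a known effect, no restart after one bolus | met on timing |

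If all bullets are needed, no level fits. If any bullet is enough, three levels fit at once: the event counts as related, but the scale cannot separate its own levels. A third reading treats the bullets as factors the investigator weighs. The event can then be rated 'possibly', but the absence of prior knowledge counts against it, and two careful raters may differ. No reading gives one definite answer.

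**Step 2: compare with the rest of the protocol.** The test in 11.1.8.1 asks for evidence suggesting causation and does not require that the effect be known. Section 11.1.8.4 assumes a suspected reaction can be missing from the IB. Criterion 5.I.b assumes a thromboembolic event can be rated possibly related, although 8.2.1 describes an antithrombotic drug and 8.2.3 reports no procoagulant effect of free drug in fluid phase. All three leave room for unexpected related events; the table in 11.1.8.3 gives them no clear place.

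**Step 3: count the criteria that use the rating.** The lettered criteria in 10.4.1.4 are 4a and 4b (2), 5.I.a to 5.I.e (5), and 5.II.a and 5.II.b (2): 2 + 5 + 2 = 9. Relatedness enters 4a, 4b, 5.I.b, 5.I.c, 5.II.a and 5.II.b, which is 6 of 9. Criteria 5.I.a, 5.I.d and 5.I.e need no causality rating. Protocol 10.4.4.2 also gives possibly related events of grade 3 or above as an example when describing emergency unblinding. Table 14.3.1.3 has five relationship columns and none for an event that could not be classified.

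**Step 4: illustrate the size.** The plan states no figure to reproduce. Each cohort has 4 active subjects. Assume a true risk *p* per active subject, a chance *q* that an event is rated at least 'possibly', independent subjects, and at most one such event each. Neither *p* nor *q* comes from the documents.

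- One-subject rules (5.I.b, 5.I.c): 1 − (1 − pq)^4
- Two-subject rules (5.II.a, 5.II.b): 1 − (1 − pq)^4 − 4pq(1 − pq)^3

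| p | ≥1 of 4, q = 1 | ≥1 of 4, q = 0.5 | ≥2 of 4, q = 1 | ≥2 of 4, q = 0.5 |
|---|---|---|---|---|
| 0.05 | 18.5% | 9.6% | 1.4% | 0.4% |
| 0.10 | 34.4% | 18.5% | 5.2% | 1.4% |
| 0.25 | 68.4% | 41.4% | 26.2% | 7.9% |
| 0.50 | 93.8% | 68.4% | 68.8% | 26.2% |

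For example, with p = 0.25 and q = 0.5, pq = 0.125 and 1 − 0.875^4 = 0.414. With q = 0, every entry is zero.

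**The case against.** A reader might infer that a novel event, and in particular the thromboembolic event in 5.I.b, cannot be rated related at all, so that the rule can never be met. The documents do not support that.

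- It requires every bullet to be mandatory, which the table does not say. Read that strictly, other levels fail too. 'Unrelated' would need implausible timing even for an obvious injury soon after dosing. 'Possibly' would need an equally likely rival cause even for a known effect. 'Likely' would need the drug to be restarted after a single bolus. This suggests the bullets were meant as guides.
- 'Possibly' asks only for correspondence with what is known, which is broader than a known effect and can include mechanism. Section 8.2.4 describes inactivation of factors Va and VIIIa and prolonged aPTT, so bleeding can be argued to correspond. Thromboembolism is less clear, but the drug is a thrombin analogue and 10.4.1.4 itself treats both events as ratable 'possibly'.
- What is known is set out in full in the IB, which is not available here.
- Other safeguards do not use the rating. Serious events are reported whatever the causality, and the primary endpoint counts all TEAEs. The investigator reviews safety data before each escalation. If there is concern, the safety review committee can add evaluations or repeat a cohort with no relatedness test.

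These points stand. They remove the claim that related ratings are impossible, and they limit the harm. They do not supply a combination rule, reconcile 11.1.8.3 with 11.1.8.1 and 11.1.8.4, or protect the six criteria that use the rating.

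**Conclusion.** The concern holds as a gap and an internal conflict, not as a bar on related ratings. Every related level refers to prior knowledge, the bullets have no combination rule, and a novel event with plausible timing and no better explanation has no clear category. Such events may be rated inconsistently and may not count in 6 of the 9 lettered criteria or in the relationship columns of Table 14.3.1.3. Criteria 5.I.a, 5.I.d and 5.I.e, serious event reporting and the overall TEAE counts are unaffected.

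The loss need not be total to matter: if half of such events were rated related, a one-subject rule would be met 41% of the time rather than 68% at a 25% risk, and 18.5% rather than 34% at a 10% risk. Those risks and the one-half are assumptions chosen to show scale. The zero that follows if no such event could be rated related depends on the mandatory-bullet reading and should not be presented as a finding.

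**What to change.** Amend the table in Protocol 11.1.8.3 so that it agrees with 10.4.1.4, 11.1.8.1 and 11.1.8.4:

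1. Define 'possibly' by the reasonable-possibility test of 11.1.8.1, for instance plausible timing with no more likely alternative cause.
2. Treat agreement with known effects or the IB as supporting information, not as a requirement.
3. State how the bullets combine within each level.
4. State that lack of prior knowledge is not a ground for denying a related rating.

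The thresholds in 10.4.1.4 stay as they are, and Table 14.3.1.3 keeps its five columns. The cost is a few words in one protocol table and matching text in the CRF completion guide. The downside is that somewhat more events may be rated possibly related, so relatedness-based criteria may be met more often, including the two that need only one active subject.

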#### Severity of AE:

Severity rating used during the study will be based on the toxicity grading scale tables present in the FDA (Center for Biologics Evaluation and Research) toxicity grading scale for healthy volunteers 4-point severity scale (Grade 1, 2, 3 and 4) [8].

The following definitions for rating severity will be used for AEs not identified in the guidance:

Mild (Grade 1)	The AE does not interfere with daily activity.
Moderate (Grade 2)	The AE interferes with daily activity, but no medical intervention is required.
Severe (Grade 3)	The AE prevents daily activity and requires medical intervention.
Potentially Life-threatening (Grade 4)	Emergency room visit or hospitalization is required.

#### 11.1.8.4 Serious Adverse Events

If any AEs are serious, as defined by the FDA Code of Federal Regulations (CFR), Chapter 21, special procedures will be followed. All SAEs will be reported to the Sponsor via fax or e-mail within one working day of becoming aware of the event, whether or not the serious events are deemed drug-related. All serious event reporting will adhere to 21 CFR 312.32 for Investigational New Drugs (IND) and to the Guidance for Industry and Investigators: Safety Reporting Requirements for INDs and BA/BE, dated December 2012 [7]. The IRB will be notified of the Alert Reports as per FDA regulations.

A SAE is any AE or suspected adverse reaction that in the view of either the PI (or designee) or Sponsor, results in any of the following outcomes: Death, a life-threatening adverse event, inpatient hospitalization or prolongation of existing hospitalization, a persistent or significant incapacity or substantial disruption of the ability to conduct normal life functions, or a congenital anomaly/birth defect. Important medical events that may not result in death, be life-threatening, or require hospitalization may be considered serious when, based upon appropriate medical judgment, they may jeopardize the patient or subject and may require medical or surgical intervention to prevent one of the outcomes listed in the above definition. Examples of such medical events include allergic bronchospasm requiring intensive treatment in an emergency room or at home, blood dyscrasias or convulsions that do not result in inpatient hospitalization, or the development of drug dependency or drug abuse.

Life-threatening is defined as an AE or suspected adverse reaction that in the view of the PI (or designee) or Sponsor, its occurrence places the patient or subject at immediate risk of death. It does not include an AE or suspected adverse reaction that, had it occurred in a more severe form, might have caused death.

Unexpected is defined as an AE or suspected adverse reaction that is not listed in the IB or is not listed at the specificity or severity that has been observed; or is not consistent with the

risk information described in the general investigational plan or elsewhere in the current application, as amended.

If a SAE occurs to a subject on this study, contact the Sponsor personnel listed in [Section 3](#).

## **11.2 Pharmacodynamic Assessment – APC-PCI**

### **11.2.1 Blood Sampling and Processing**

For all subjects, blood samples for the determination of APC-PCI will be collected in sodium heparin blood collection tubes at scheduled time points as delineated in the Study Events Flow Chart ([Section 6](#)) and processed to plasma.

The sample times and Hour 0 are in relation to start of IV bolus.

At the end of the study, platelet poor plasma samples obtained by centrifugation of heparinized blood will be shipped to the analytical laboratory for analysis.

Instruction for blood sampling, collection, processing, and sample shipment will be provided separately.

### **11.2.2 Analytical Method**

Plasma sample analysis for APC-PCI will be performed by Celerion using qualified bioanalytical methods.

## **11.3 Pharmacodynamic Assessments – Real-Time aPTT and protein C**

### **11.3.1 Blood Sampling and Processing**

Blood samples for real-time aPTT and protein C will be analyzed by Aronora on site. Samples will be collected in blood collection tubes containing 3.2% sodium citrate at scheduled time points as delineated in the Study Events Flow Chart ([Section 6](#)) by a Celerion employee, and transferred directly to an Aronora employee for sample processing as per their internal procedures.

At the end of the study, platelet poor plasma samples obtained by centrifugation of citrated blood will be shipped to the Sponsor for their internal analyses.

### **11.3.2 Analytical Method**

Citrated plasma sample analysis for real-time aPTT and protein C will be performed by the Sponsor using their internal method.

## 11.4 Blood Volume for Study Assessments

**Table 3: Blood Volume during the Study**

Sample Type	Number of Time Points	Approximate Volume per Time Point * (mL)	Approximate Sample Volume Over Course of Study (mL)
Screening laboratory safety tests (including hematology, serum chemistry, serology, and coagulation), FSH (for postmenopausal female subjects only) and serum pregnancy (for female subjects only).	1	16	16
On-study hematology, serum chemistry (this includes serum pregnancy for female subjects only when scheduled at the same time)	2	12.5	25
On-study coagulation (aPTT, PT/INR, fibrinogen, and, if scheduled at the same time, thrombin time)**	10	3.5	35
Thrombin Time only	1	3.5	3.5
Blood for plasma immunogenicity (E-WE thrombin plasma ADA) (Celerion)	3	9	27
Blood for serum immunogenicity (WT thrombin serum ADA) (Celerion)	3	5	15
Real-time aPTT: Citrated (3.2%) blood for aPTT (Aronora)	8	2.7	21.6
Real-time protein C: Citrated (3.2%) blood for protein C (Aronora)	4	1.8	7.2
Blood for APC-PCI (Celerion)	8	4	32
Total Blood Volume (mL)→			182.3***

\* Represents the largest collection tube that may be used for this (a smaller tube may be used).

\*\* If by Day 14 aPTT and/or thrombin time values have not returned within  $\pm 10\%$  of the baseline value or the normal range, sampling will continue every 7 days ( $\pm 2$  days) until the  $\pm 10\%$  of baseline value or to the normal range is reached or a maximum of ~500 mL of blood is collected from the subject. Subjects who terminate the study early will also be asked to return every 7 days ( $\pm 2$  days) for aPTT and thrombin time monitoring until values return within  $\pm 10\%$  of baseline value or the normal range.

\*\*\* If additional safety or PD analysis is necessary or if larger collection tubes are required to obtain sufficient plasma/serum for analysis, additional blood may be obtained (up to a maximum of 50 mL).

